Midpoint IIP review: Therapists will review the child on the individualized intervention plan (IIP) developed after baseline assessment and plan for further intervention.

Final Reviews and Assessments: Visit 12 to 14

The final reviews and assessments will be conducted across three sessions, which can take place in any order depending on the participant's availability and therapist's schedule.

Final Review with Therapist: The child will be evaluated on the baseline assessment measures. Parents will also be given a parent satisfaction survey, cost survey and FEIQoL survey to complete. If parents are unable to complete the surveys during their clinic-based session, they will be sent the surveys through email or asked to answer the questions over a phone call. For children in the telerehab group, there will be a VC review in addition to the clinic-based assessment.

Nurse Assessment: The child will be evaluated on MSEL. The Parental Stress Index will be administered as part of this assessment.

Psychologist Assessment: VABS-III will be administered to the parent for this assessment.

Final Paediatrician review: Visit 15

[figure not shown]
This last paediatrician visit is for the paediatrician to share the reports on the evaluations, discuss progress and further needs of child and family.

Transfer to Early Intervention Programs

CDU provides interim therapy for children pending their enrolment into an EIPIC (or private early intervention service). Under normal circumstances, the child does not receive any intervention from EIPIC in the first 10 weeks on enrolment as the child is being assessed. In this transition period, the child continues to receive CDU intervention per standard clinical practice. As such, children in this study will continue to receive intervention for 10 weeks after EIPIC enrolment. Similarly, children who has been transferred to a private intervention service will continue to receive intervention per the study protocol as long as they have not started receiving intervention at the private service.

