
a. Is the intervention as effective as the standard care model in improving the level of function among children with ASD?
	
Mullen's Scale of Early Learning (MSEL)
	
MSEL is a standardized developmental assessment to examine developmental skills of children aged birth to 68 months on gross motor and cognitive scales using 5 subscales: Gross Motor, Visual Reception, Fine Motor, Expressive Language, and Receptive Language. T scores, percentile ranks, and age equivalents can be computed for the five scales separately.
 
For each scale, the assessment derives a T-score with a mean of 50 and standard deviation of 10, a percentile score, and an age equivalent indicating at what developmental age the child is performing. An early learning composite (ELC) score is calculated from the total of scores on all scales (excepting the gross motor scale) with a mean of 100 and standard deviation of 15. T scores for subscales have a mean of 50 (SD: 10). (Bacon et al,2014)
 
For children suspected of ASD, MSEL is often chosen because of its wide age range and 5 subscales that allow separate assessment of verbal and non-verbal abilities.
 
Previous studies of intervention efficacy has used MSEL subscale scores for greater granularity of analysis, to understand the impact of intervention on specific functions of the child and separate assessment of verbal and non-verbal activities (Vismara et al, 2009).
	
Differences in scores on the subscales of the MSEL from baseline to program conclusion will be calculated and compared between the two intervention groups

	
Vineland Adaptive Behaviour Scales (VABS-III)
	
VABS-III is a standardised assessment tool that utilises a semi-structured interview format to measure adaptive behavior. The main domains are: Communication, Daily Living Skills and Socialization. The Vineland-III is used for measuring an individual's daily functioning, progress planning and monitoring.
	
Differences in scores on VABS-III in communication, socialisation and daily living from baseline to program conclusion will

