		VABS-III provides a measure of adaptive skills used to cope with challenges of daily living. A caregiver completes a questionnaire regarding the individual's current level of functioning across three domains: communication, daily living skills and socialization. The Vineland Scales are applicable to children with and without delays from birth to 18 years, 11 months. All scales use standard scores with a mean of 100 and a standard deviation of 15, a percentile score, and an age equivalent indicating at what developmental age the individual is performing. Scores on the three domains are combined to obtain an overall adaptive behavior composite (ABC) with a mean of 100 and a standard deviation of 15.	be calculated and compared between the two intervention groups
b. Is the tele-health intervention as effective as standard care in improving parent-child interaction?	Joint Engagement Rating Inventory (JERI)	
JERI measures:
 
 - joint engagement, - communication dynamics and - shared topics in a caregiver-child interaction on a 7-point likert scale (Adamson & Bakeman, 2012). 
This is a structured assessment of joint attention and communication. It measures multiple aspects of caregiver-child interactions and identifies the specific triadic elements in engagement which are effected in Autism. This has the advantage of being a standardized assessment of social communication. It provides an insight into the dynamics of caregiver child interactions which will help in intervention planning to enhance the quality of caregiver-child engagement.
	
Change on the JERI will be tracked by calculating the changes in:
 
 - nature of joint engagement, - child's participation in joint engagement with caregiver, - caregiver behaviours during engagement and - the range and quality of the caregiver-child interactions 
from baseline to program conclusion and compared between the two intervention groups

c.	Parenting Stress Index-	PSI-SF (Abidin, 1995) is an abbreviated version of the PSI. It is a 36-item self-report questionnaire assessing the level of relative stress in a parent-child	Change on the PSI-SF across 3 domains:

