Patients will be recruited for the program after obtaining a preliminary diagnosis of ASD from the developmental paediatrician. ADOS-2 will be administered to confirm the diagnosis and thus participation in the research study. We will not be advertising this study to the public.

Pilot

An initial pilot feasibility study with 6 children and families will be conducted at the start of the project to identify any practical issues or weaknesses in the program or protocol before full scale evaluation.

Sample Size Calculation

The randomized trial is designed as a non-inferiority study to compare the changes in MSEL between 2 interventions. We expect that the change in MSEL score for the subjects in the new intervention arm will be slightly better than that in the control arm by 1.5 units. Assuming the SD of changes in MSEL score is 15 units, with 5 units as the non-inferiority margin, based on a one-sided test with 80% power and 5% significance level, it is sufficient to recruit 132 subjects (66 in each arm). We decided to recruit 200 subjects in total (100 in each arm) after considering withdrawals and lost to follow up. The computation was performed using a proprietary software programmed in R.

Randomisation Process and Blinding

Computer-generated randomisation will be used to randomly assign the participants to one of the intervention groups. Block randomisation will be used to allocate the recruited subjects into one of the interventions. A randomisation list will be generated by the study statistician and envelopes will be prepared. Although the allocation of intervention will be concealed and the study team will not know in advance which subject will receive which intervention, the blinding will not be possible once the intervention is assigned. Assessors of the initial and final MSEL were not told of the intervention status of the patient to avoid bias in outcome assessment. Blinding of the parents is not possible in the context of this study. Phone calls will be made if necessary to confirm appointments and/or before commencing consultation over video conference in the Telerehab group. Parents in both study arms will be encouraged to spend 2h per week in quality interactions with their children.

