Children who meet the inclusionary criteria will be randomly assigned to the standard or telerehab group of the study. Parents will be informed of the randomisation assignment and clinical diagnostic impression on ADOS. Baseline evaluation measures – Mullen's Scales of Early Learning (MSEL), Vineland Adaptive Behaviour Scales (VABS-III), Parenting Stress

Index (PSI-SF), Joint Engagement Rating Inventory (JERI) and FEIQoL (Families in Early Intervention Quality of Life) - will be completed for all.

Data Collection Time Points

The child and parents' skills will be recorded at 4 data points (baseline; 2 midterm reviews; final review) and progress tracked on the IIP, JERI and FSC. Parent questionnaires will be given at the end of the intervention to evaluate parents' experience with the technology used in the sessions, using a Likert Scale, and to evaluate their experience as *providers* of intervention services to their child. Video analyses will be performed by external raters. Inter-rater reliability will be calculated based on the assessments of raters (number of agreements/number of agreements plus disagreements). Hospital resource use pertaining to the intervention will be recorded at each point as well as healthcare expenditures and household resource use, travel expenses and caregiver time spent.

All clinical data will be collected in the case record form designed for the collection of data for the study. For the various assessment tools that will be used, data will be collected on the assessment tool itself, which will serve as the source of that data.

All data will be later transcribed to excel sheets or other relevant databases as soft data for statistical analysis. The data will be coded to remove any patient identifiers before sharing with the statistician for analysis.

Exit Review for Early Withdrawals

If the participant has completed their first block of intervention and requests to withdraw from the study before their final reviews and assessments (Visit 12 to 14), they will be presented with the option to come back to the clinic for an exit review before withdrawing. In the exit review, the child will be assessed on MSEL, parental stress index, parent satisfaction survey, cost survey, FEIQoL and VABS. Specific to the children in the telerehab arm, an additional video recording of parent-child interaction will be done through VC. However, participants can opt to not come back for the exit review and withdraw from the study immediately.

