Parent-delivered therapy (home-based)				
Visit 9	Midpoint IIP Review with Therapist (clinic based)	60	Midpoint IIP Review with Therapist (clinic based)	60
3 rd block of intervention	Clinic-based intervention x 6	60 x 6	Video conference-based intervention (VCBI) x 2	45 x 2
	Parent-delivered therapy (home-based)			
Visit 10-11	Fifth Paediatrician visit Midpoint Review by paediatrician (clinic based or teleconsultation)			30
	
 • Child's profile, progress • Child and Family's needs • Appropriate recommendations and referrals (if needed) 			
	Review with Therapist (clinic based)			60
	
 • Foundational skills curriculum – Child's development profile • Joint Engagement Rating Inventory (JERI) • Cost Survey 			

4 th intervention block	Parent-delivered therapy (home-based)	Video conference-based intervention (VCBI) x 6	45 x 6
		Parent-delivered therapy (home-based)	
Visit 12-14	Final Review with Therapist (clinic based)		90
	
 • Foundational skills curriculum (FSC) assessment • Joint engagement rating inventory (JERI) • Family Early Intervention Quality of life survey (FEIQoL) • Cost Survey 		
	Additional Indicators to baseline:		
	
 • Parent Satisfaction Survey 		
	Final Nurse Assessment (clinic based)		120
	
 • MSEL & PSI 		
	Final Psychologist Assessment (teleconsultation)		60
	
 • VABS-III 		
		Video conferencing observation (FSC, NDBI-Fi)	30
Visit 15	Sixth Paediatrician visit (final visit)		30
	Paediatrician to share reports and discuss progress and further needs of child and family		
Post-interview will be conducted for eligible and chosen participants after intervention is completed, or after participant has transitioned to EIPIC.			45
End of study			

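### The stated assessor blinding stops at the MSEL: the final VABS-III and the exit-review assessments are left uncovered although withholding the arm there would be cheap

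*Combined protocol and SAP*

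**What the plan says.** Randomisation Process and Blinding starts from the position that "the blinding will not be possible once the intervention is assigned" and makes one exception: "Assessors of the initial and final MSEL were not told of the intervention status of the patient to avoid bias in outcome assessment". It adds that "Blinding of the parents is not possible in the context of this study".

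Under Final Reviews and Assessments, the closing measurements are split over three sessions: one with the therapist, one with a nurse (MSEL and the parenting stress questionnaire) and one with a psychologist. For the psychologist session, "VABS-III will be administered to the parent for this assessment". Annex 1 lists it as a separate 60-minute teleconsultation. Neither place mentions blinding.

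For families who leave early, Exit Review for Early Withdrawals says: "In the exit review, the child will be assessed on MSEL, parental stress index, parent satisfaction survey, cost survey, FEIQoL and VABS". It does not name the assessors or say what they know.

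The indicators table describes the instrument in two ways. First, "VABS-III is a standardised assessment tool that utilises a semi-structured interview format to measure adaptive behavior". Then, in the same entry, "A caregiver completes a questionnaire regarding the individual's current level of functioning across three domains".

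**The concern.** The plan's reason for keeping MSEL assessors unaware of the arm applies equally to any outcome that a member of staff scores by judgement. In a parent interview, someone who knows how the sessions were delivered can probe more or less, or give more or less credit. That difference would pass straight into the between-arm change in VABS-III. Quantitative Outcomes compares the change in adaptive score between arms, and the cost-effectiveness objective names VABS as an effect measure, so both would carry it.

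The gap looks avoidable. The psychologist sees the parent in a session apart from the therapist's review, and nothing in the documents suggests that this psychologist needs to know the arm. Nor does the plan ask parents to keep the arm to themselves or record whether they did. The stated MSEL blind therefore cannot be verified either, since the nurse administers the parenting stress questionnaire in the same session.

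**Working it through.** **1. What the plan was sized on.** The inputs in Sample Size Calculation are SD of change 15, margin 5, expected advantage 1.5, one-sided 5%, power 80%. Then n per arm = 2 × 15² × (1.645 + 0.842)² / (5 + 1.5)² = 450 × 6.18 / 42.25 ≈ 65.9, so 66 per arm and 132 in total, as stated. These figures are for MSEL. No margin, SD or power is given for VABS-III. Wider blinding would not change the sample size.

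**2. Where blinding is stated and where it matters.** Baseline Assessments places MSEL and VABS at Visits 2 to 3 and allocation at Visit 4.

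| Assessment | Assessor | Relative to allocation | Arm withheld by the text? |
|---|---|---|---|
| Initial MSEL | Nurse | Before | Yes, but nothing to withhold yet |
| Initial VABS | Psychologist | Before | Not stated, not needed |
| Final MSEL | Nurse | After | Yes |
| Final VABS-III | Psychologist | After | Not stated |
| Exit-review MSEL | Not named | After | Only if read as that child's final MSEL |
| Exit-review VABS | Not named | After | Not stated |

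The only assessment that the sentence clearly protects after allocation is the final MSEL.

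**3. Whether exit-review data can reach the analysis.** No section says that they do. The analysis is per-protocol and requires 80% of intended sessions, which removes many early leavers.
- Control arm, on the 16 sessions described under Intervention: Standard Program: 0.8 × 16 = 12.8, so 13 sessions. A child leaving after blocks 1 and 2 has 6 + 4 = 10 and is excluded.
- Control arm, on the wording in Protocol Deviation and Per-protocol Analysis: 8 of 10 sessions. The same child is retained.
- Telerehab arm: 2 + 16 = 18 sessions, and 0.8 × 18 = 14.4, so 15 sessions. After blocks 1 to 3 a child has 6 + 4 + 2 = 12 and is excluded. Only a leaver late in block 4 could qualify.

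The contribution is therefore limited but not nil. The 10-session and 16-session statements for the control arm contradict each other and must be reconciled.

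**4. Size.** The documents give none. For scale only, assume that knowing the arm shifts scoring by 0.1 to 0.2 SD, which is 1.5 to 3 points on a scale with SD 15, and borrow the MSEL change SD and 66 per arm. Then SE = 15 × √(2/66) = 2.61, the 95% half-width is 1.96 × 2.61 = 5.12, and the shift is 1.5/5.12 = 29% to 3/5.12 = 59% of it. Both the shift and the use of this SD for VABS are assumptions. With no VABS margin, the percentages map to no decision.

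**The case against.** The strongest reply is that the plan protects the measure on which its conclusion rests. MSEL alone is powered, carries the only non-inferiority rule and is called the primary outcome in the cost-effectiveness section. This stands. A reader might infer from the indicators table that VABS-III is co-primary, because it sits beside MSEL in a column headed as primary indicators. That heading covers all eight questions, including satisfaction, family quality of life and costs, so it does not support that inference.

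Second, if the caregiver fills in a questionnaire, there is little for an interviewer to bias. This stands as a condition. The psychologist session, in which the instrument is administered to the parent, favours the interview reading but does not settle it.

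Third, the parent knows the arm, supplies the answers and may disclose the arm in conversation. So blinding the psychologist is harder to keep than blinding a direct test of the child, and removes only part of the bias. This stands too.

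Fourth, the exit MSEL may already count as a child's final MSEL. That is a fair reading, but it is not written down, and no such reading rescues the exit VABS.

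Fifth, timing. The protocol is version 8, dated 19/08/2022, and Table 4 shows no further enrolment in Year 5, with the study ending on 31 May 2023. Some final assessments may already be done; the number is not given. An amendment cannot blind those retrospectively. This limits the remedy but does not remove the gap.

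**Conclusion.** The point holds as a modest and cheaply closed gap. The stated blinding does not reach the final VABS-III, the exit-review VABS or, arguably, the exit-review MSEL. VABS-III is a non-powered outcome, but it is compared between arms and used in the cost-effectiveness analysis. The risk of interviewer bias depends on the instrument being interviewer-administered, which the plan leaves contradictory. Its size and direction are unknown.

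Two stronger readings are not supported. A reader might infer that the psychologist is told the arm. The plan is silent, so the most that can be said is that the psychologist may know. A reader might also infer that the non-inferiority conclusion is compromised. It rests on MSEL, whose final assessors are covered by the stated safeguard; what is missing there is a record of whether the blind held.

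The external video raters also have no stated blinding, and JERI is a cost-effectiveness outcome. That is a separate matter, not weighed here.

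**What to change.** For assessments still to be done, amend Randomisation Process and Blinding along these lines: assessors of the final and exit-review MSEL, and of the final and exit-review VABS-III, are not told the study arm and do not open therapy notes before scoring; parents are asked at booking not to mention how their sessions were delivered; each assessor records whether the arm was disclosed, and this is reported by arm.

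For assessments already done, report whether the VABS assessor knew the arm, and do not describe those assessments as blinded.

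Reconcile the two descriptions of VABS-III in the indicators table, so that it is clear whether an interviewer scores it.

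The cost is a short amendment, a line in the booking script and a tick box, with the same staff, visits and sample size. There are two downsides. The psychologist loses the option of consulting therapy notes before the interview, and procedures may differ between earlier and later assessments, which the report should state. Bias from the parent as informant remains and should be acknowledged as a limitation.

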At the start of the session, the parents' progress from the past topic and any other updates will be reviewed and discussed for 5–10 minutes. This is then followed by a 10-minute parent-child play activity. The activity allows the therapist to observe the parent's competency in implementing intervention (i.e. the goals and effective use of strategies) from the previous session's coaching. Based on observations made, the therapist will coach further to strengthen parent's confidence and competency in using strategies to facilitate the attainment of specific learning objectives in the IIP. During the final 10–15 minutes of each session, the therapist will seek feedback from the parent to understand parent's clarity, comfort and confidence in implementing the intervention plan and provide further input and information if required. The therapist will also address any challenges faced or anticipated in the context of implementing the intervention in the home context. The therapist will discuss with parents to implement the intervention plan using at least two play or daily routines (naturally occurring opportunities) identified by the parent. Adult learning principles will be adopted by

the therapist to facilitate active participation in planning and intervention implementation. For clinic-based sessions, an additional 15 minutes is allocated to allow the child and parents to settle down and transit into and out of the therapist's room.

Data collection: For all subjects, video recordings of parent child interactions will be taken at 4 specific time points, namely Baseline, two Midterm reviews and Final review. Specific to the children in the telerehab arm, an additional video recording of parent-child interaction will be done through VC for each on-site review session, totalling 8 video recording time points throughout the program's duration. Recorded videos will be downloaded and transferred to a password encrypted hard drive authorized by the institution data protection and security teams. These recordings can only be accessed by authorized team members with institutional accounts and external raters. They will be used for evaluation on the JERI, NDBI-Fi and for inter-rater reliability assessment.

Parent-delivered therapy (Home-based)

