At the end of each intervention session and at the end of each intervention block, a joint discussion will be held to craft a plan for parents to implement. This will include the functional goals to be embedded, specific strategies to be used that the parent has been coached in and the home routines that the parent plans to implement. Intervention related resources such as description of strategies and examples of embedding within routines and documents on the plan will be shared with parents for their reference.

Program Timeline

While set timeframes for assessments, intervention and reviews are important, this study will be implemented under routine operational conditions of the clinical service. The standard practice of having the same therapist for each session for continuity will be adopted. Scheduling challenges are an unavoidable field condition. This is compounded by the need for rescheduling of sessions at times, such as when a child/family member or therapist is unwell. For these reasons, the duration of time to complete each intervention block may vary slightly for each child. It may also vary between the intervention and control groups.

In general, where delays from scheduling occur, each child will move to the next phase of the study (i.e. intervention and follow-up reviews) only when they have completed all planned sessions in the previous phase (e.g., intervention will only begin after all baseline assessments have been completed). These are recognised as limitations of the study design and will be considered when interpreting the study findings.

Follow-up and Review (Standard Program and Telerehab Program)

Midterm Progress Review: Visit 7 to Visit 11

Paediatrician Review (two visits): The paediatrician will review the child's general developmental profile, progress and child and family needs. The clinician will make appropriate recommendations and referrals as needed.

Therapist Review (two visits): Therapists will review the child's developmental profile on the FSC and JERI to track progress on the intervention plan and for program evaluation purposes. A cost survey will also be conducted with parents during these reviews by a member of the study team to identify any changes to household income and cost burden. If parents are unable to complete the survey during their session, they will be sent the survey through email or asked to answer the questions over a phone call.

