Protocol deviation is defined as any divergence from what was pre-planned and approved by the institutional review board. As the study is conducted as part of routine care and operations, there are practical constraints that may cause protocol deviations to occur. Rescheduling of appointments by the parents (e.g. due to work constraints, child's sickness, other events) or defaulting appointments is inevitable. Hence, for per-protocol analyses, we will only exclude participants with major protocol deviation, which will be defined as participants who do not complete 80% of the intended therapy sessions allocated for their study arm. This means that a control arm participant must attend at least 8 out of 10 clinic-based sessions. For the remaining 2 sessions, participants can either be attending it through video-conferencing (due to the COVID-19 pandemic) or miss the appointment.

Quantitative Outcomes

For the randomized trial, since the study is a non-inferiority study, statistical analysis will be carried out on a per-protocol basis. Subjects with any major protocol deviation as defined above will be excluded from the final analysis.

All demographic, clinical and cost characteristics will be analysed descriptively. Mean (SD) or median (range), whichever is more appropriate will be reported for numerical variables, while N (%) will be reported for categorical variables. 2-sample t-tests, or Mann-Whitney U tests will be used to compare the change of MSEL score between 2 arms. Mean difference and 95% CI will be estimated. If the lower boundary of the 95% CI is more than -5, non-inferiority will be declared. Changes in the quality of parent-child engagement, parental stress index score, and adaptive score will be compared by using either a 2-sample t-test, or a Mann-Whitney U test, whichever is more appropriate. Linear regression will be used to adjust for any covariates.

Cost-Effectiveness Analysis

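### JERI is rated in clinic at four visits, but the stated between-arm comparison uses only final-minus-baseline change, with baseline JERI not named as a covariate

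*Combined protocol and SAP*

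**What the plan says.** **Schedule.** Data Collection Time Points says that child and parent skills "will be recorded at 4 data points (baseline; 2 midterm reviews; final review) and progress tracked on the IIP, JERI and FSC". The data-collection paragraph under Intervention: Telerehab Program says that, for all subjects, "video recordings of parent child interactions will be taken at 4 specific time points, namely Baseline, two Midterm reviews and Final review". Annex 1 places JERI at Visits 5, 7-8, 10-11 and 12-14 in both arms.

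**Use of the midterm ratings.** Follow-up and Review says: "Therapists will review the child's developmental profile on the FSC and JERI to track progress on the intervention plan and for program evaluation purposes". No between-arm analysis of them is described.

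**Endpoint and test.** The Indicators and Outcomes table makes JERI the only indicator for question b and defines the outcome as change "from baseline to program conclusion and compared between the two intervention groups". Quantitative Outcomes says: "Changes in the quality of parent-child engagement, parental stress index score, and adaptive score will be compared by using either a 2-sample t-test", with Mann-Whitney as the alternative. The only model mentioned is one sentence: "Linear regression will be used to adjust for any covariates". The covariates are not named. No repeated-measures model or missing-data method appears. Quantitative Outcomes sets the analysis on a per-protocol basis. The Cost-Effectiveness Analysis also uses JERI.

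**Early leavers.** At the optional exit review, "the child will be assessed on MSEL, parental stress index, parent satisfaction survey, cost survey, FEIQoL and VABS". JERI is not listed. The next sentence adds: "Specific to the children in the telerehab arm, an additional video recording of parent-child interaction will be done through VC". Under Transfer to Early Intervention Programs, children who move to an EIPIC are still to have their midterm and final assessments.

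**The concern.** A change score needs both ends. A child with a baseline and one or two midterm ratings but no final rating has no change score, and the plan gives no way to impute one. The exit review does not fill the gap: it does not list JERI, it is optional, and its extra recording is made in one arm only, so it yields no rating comparable across arms. For withdrawals and missed finals, the midterm clinic ratings are then the only post-baseline JERI data that both arms share.

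Two things are at stake. One is precision, because an unadjusted change score is less efficient than a baseline-adjusted comparison. The other is robustness: if loss of the final rating is related to change, and differently so in the two arms, the comparison of those who remain is biased. A likelihood-based repeated-measures model allows loss to depend on ratings already observed.

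**Working it through.** **1. The plan's own figure.** The only stated sample size is for MSEL: SD 15, margin 5, expected advantage 1.5, one-sided 5%, power 80%.

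n per arm = 2 × (1.645 + 0.842)² × 15² / (5 + 1.5)² ≈ 65.9, so 66 per arm and 132 in total. This matches. Recruiting 200 implies an allowance of 1 − 132/200 = 34%. It is an MSEL recruitment allowance, borrowed here only as one scenario for missing JERI finals.

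**2. Assumptions.** SD 1 at every visit; the same correlation r between any two visits; 100 per arm. Last clinic rating: final 66, midterm 2 10, midterm 1 12, baseline only 12. This split is assumed.

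**3. Variance of the final-visit arm difference.**
- Planned change score, complete cases: 2 × 2(1 − r)/66 = 4(1 − r)/66.
- Baseline-adjusted, complete cases: 2(1 − r²)/66. Its ratio to the change score is (1 + r)/2.
- Repeated-measures model: sum n·X′V⁻¹X over the dropout patterns, with a common baseline mean and arm-by-visit means, then invert and take the final-visit contrast.

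| r | Change score | Baseline-adjusted | Repeated measures | Adjusted / change | Repeated / change | Repeated / adjusted |
|---|---|---|---|---|---|---|
| 0.5 | 0.03030 | 0.02273 | 0.02193 | 0.75 | 0.724 | 0.965 |
| 0.6 | 0.02424 | 0.01939 | 0.01855 | 0.80 | 0.765 | 0.956 |
| 0.7 | 0.01818 | 0.01545 | 0.01466 | 0.85 | 0.806 | 0.948 |

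Most of the gain is baseline adjustment. The last column isolates what the midterm ratings add: about 4–5%.

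**4. Range for the midterm contribution.**
- No missing finals: the ratio to the baseline-adjusted analysis is exactly 1, so there is no gain.
- 10% missing (90/3/3/4 per arm): ratio 0.987–0.991, about 1%.
- Planned per-protocol set, where the only recoverable children are the 10 controls last rated at midterm 2 (step 5): 1.1–1.6%.
- Correlation decaying with distance (AR(1), adjacent-visit 0.5–0.7), 34% missing as in step 2: 0.54–0.62 of the change-score variance, 0.93–0.96 of the baseline-adjusted variance.
- Most favourable case, where every child without a final has both midterms: at 34% missing and correlation 0.4–0.8 of either form, 66 complete cases per arm are worth about 69–80.

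**5. Interaction with the per-protocol rule.** Annex 1 gives these session counts, assuming full attendance.
- Control: 6 + 4 = 10 of 16 (62.5%) by the first midterm review; 6 + 4 + 6 = 16 of 16 by the second.
- Telerehab: 2 + 4 + 4 + 2 = 12 of 18 (67%) by the second midterm review.

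The 80% thresholds are 0.8 × 16 = 12.8 and 0.8 × 18 = 14.4 sessions. A control child who leaves after the second midterm review is per-protocol, with three JERI ratings and no change score. A telerehab child who leaves at the same point is excluded. The rule thus treats late leavers differently by arm. The protocol's worked example, 8 of 10 clinic sessions for a control child, does not fit the 16 control sessions stated elsewhere; the passages must be reconciled.

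**The case against.** Several points on the other side stand.

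- **Midterm ratings discarded.** A reader might infer that they are thrown away. They are not: therapists use them to track the plan. They are absent only from the stated between-arm analysis.
- **No exit data at all.** A reader might infer that a family that leaves has no later JERI information. For telerehab this is unsettled. The protocol says that its recordings are used for JERI and NDBI-Fi ratings, whereas Annex 1 labels the video-conference observations FSC and NDBI-Fi. What holds is that the exit review gives nothing comparable in the control arm.
- **All who leave the programme are lost.** Children transferred to an EIPIC are still to be assessed, so the loss concerns withdrawals and missed finals.
- **The planned test is valid only if those lost are a random subset.** That is too strong. Similar selection in both arms also leaves the contrast unbiased, and regression on baseline would allow for loss related to baseline.
- **The regression sentence already permits baseline adjustment.** It does, but it neither names baseline JERI nor makes that the main analysis.
- **The gain depends on changing the analysis set.** Correct. Within the per-protocol set the midterm contribution falls to 1.1–1.6%, and the added children are all controls. The change must therefore be disclosed.

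**Conclusion.** The point holds as a worthwhile improvement to a non-primary outcome. JERI is collected four times in both arms, and the stated comparison uses two of those occasions without naming baseline as a covariate or saying what happens to children with no final rating.

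Under the assumptions shown, the proposed model has 72–81% of the planned test's variance. It would be wrong to credit this to the midterm ratings, because baseline adjustment alone gives 75–85%. The midterms add between nothing and about 5% in the main scenarios, plus some protection when loss depends on earlier ratings. None of these sizes can be fixed more closely, since the documents give no JERI SD, correlation or missing rate.

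The main trial conclusion is not in doubt. The sample size and the non-inferiority claim rest on MSEL, which is scheduled only at baseline and at the end.

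**What to change.** Before the final analysis, amend Quantitative Outcomes for JERI as follows.

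1. Use a mixed model for repeated measures on the clinic-recorded ratings, with arm-by-visit means, unstructured covariance, and a common baseline mean (or baseline JERI as a covariate). Report the final-visit arm difference with its 95% CI. Separate arm-by-visit means also accommodate the unequal session counts at the second midterm review.
2. Fit it on all randomised children with any clinic rating. State that this departs from the plan's per-protocol set, and report the per-protocol version alongside.
3. Name the JERI score or scores to be modelled, since the indicator table lists several facets and no total. Keep a rank-based or robust analysis as a sensitivity check for skewed ratings.
4. State the missing-at-random assumption and one sensitivity analysis that departs from it.
5. Say whether the telerehab exit recording will be JERI-rated, and keep it out of the between-arm model, because controls have no counterpart.
6. Reconcile the control-arm session count in the per-protocol definition with the rest of the protocol.

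The cost is SAP wording, one standard model and a second analysis set to report and explain; no new visits or data are needed. If the t-test is kept, the plan should at least name baseline JERI as a covariate and say how children without a final rating are handled.
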